Post-Vaccination 2 evaluable	
All randomized participants who were:
 
 eligible throughout 1 month after the second dose of MenABCWY, received the investigational product at Visit 1 (for Groups 1 and 2) and Visit 4 (for Group 1) and Visit 9 (for Group 2) as randomized, had blood drawn for assay testing within the required time frames at Month 0 (Visit 1; before Vaccination 1) and at 1 month after the second MenABCWY vaccination (Visit 5 for Group 1 and Visit 10 for Group 2: window 28-42 days), had at least 1 valid and determinate MenA/C/W/Y or MenB assay result at 1 month after the second MenABCWY vaccination (Visit 5 for Group 1 and Visit 10 for Group 2), had received no prohibited vaccines or treatment through Visit 5 (Group 1) or Visit 10 (Group 2), and had no important protocol deviations through Visit 5 (Group 1) or Visit 10 (Group 2). 
An important protocol deviation is a protocol deviation that, in the opinion of the sponsor's global medical monitor, would materially affect assessment of immunogenicity (eg, participant's receipt of a prohibited vaccine or medication that might affect immune response or a medication error with suspected decrease in potency of the vaccine).

Post-Vaccination 1 mITT	All participants who received at least 1 study vaccination and had at least 1 valid and determinate MenB or MenA/C/W/Y assay result available at any time point from Visit 1 to Visit 2.
Post-Vaccination 2 mITT	All participants who received at least 1 study vaccination and had at least 1 valid and determinate MenB or MenA/C/W/Y assay result available at any time point from Visit 1 to Visit 5 for Group 1 and from Visit 1 to Visit 10 for Group 2.

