9.4.1. Immunogenicity Analyses

Primary	For each of the 4 primary MenB test strains, the percentage of participants with an hSBA titer \geq LLOQ at baseline and at 1 month after the second dose of MenABCWY will be calculated for each vaccine group. Exact 2-sided 95% CIs for the percentages will be provided using the Clopper-Pearson method.
---------	---

	
The primary analysis for the primary MenB strains is based on the post-Vaccination 2 evaluable population.
 
A supportive analysis will be performed based on the applicable mITT population. Participants will be summarized according to the vaccine group to which they were randomized. Missing serology data will not be imputed.

Secondary	
The percentage of participants in Group 1 (0- and 12-month schedule) with hSBA titers \geq LLOQ for each of the primary MenB test strains at 12 and 24 months after the second dose of MenABCWY will be summarized using the post-Vaccination 2 evaluable population.
 
The percentage of participants in Group 1 with hSBA titers \geq LLOQ for each of the ACWY test strains at 12 and 24 months after the second dose of MenABCWY will be summarized using the post-Vaccination 2 evaluable population.
 
The percentage of participants in Group 1 (0- and 12-month schedule) and Group 2 (0- and 36-month schedule) separately with hSBA titers \geq LLOQ for each of the ACWY test strains at baseline and at 1 month after the first dose of MenABCWY will be summarized using the post-Vaccination 1 evaluable population. The percentage of participants in Groups 1 and 2 separately with hSBA titers \geq LLOQ for each of the ACWY test strains at baseline and at 1 month after the second dose of MenABCWY will be summarized using the post-Vaccination 2 evaluable population.
 
Reverse cumulative distribution functions will be provided for both MenA/C/W/Y strains (1 month after the first and second dose of MenABCWY) and MenB strains (1 month after the second dose of MenABCWY) for each vaccine group.
 
Supportive analyses will be done using the applicable mITT population. Exact 2-sided 95% CIs for the percentages will be provided using the Clopper-Pearson method. Participants will be summarized according to the vaccine group to which they were randomized. Missing serology data will not be imputed.

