- Population: Participants receiving 2 doses of MenABCWY and who are in compliance with the key protocol criteria (evaluable participants).
- Variable: hSBA titer for each of the ACWY test strains.
- Intercurrent event(s): Participants will be summarized according to the vaccine group to which they were randomized. Missing serology data will not be imputed.
- Population-level summary: The percentage of participants achieving an hSBA titer  $\geq$  LLOQ (ie, hSBA titer of  $\geq 1:8$ ) for each ACWY test strain at baseline and 1 month after the second dose of MenABCWY Group 2 (0- and 36-month schedule).

For the secondary objective to describe the persistence of the MenB response following 2 doses of MenABCWY administered on a 0- and 12-month schedule, the estimand has the following attributes:

- Population: Participants receiving 2 doses of MenABCWY and who are in compliance with the key protocol criteria (evaluable participants).
- Variable: hSBA titer for each of the primary MenB test strains (A22, A56, B24, and B44).
- Intercurrent event(s): Participants will be summarized according to the vaccine group to which they were randomized. Missing serology data will not be imputed.
- Population-level summary: The percentage of participants achieving an hSBA titer  $\geq$  LLOQ for each of the 4 primary MenB test strains at 12 months and 24 months after the second dose of MenABCWY in Group 1 (0- and 12-month schedule).

For the secondary objective to describe the persistence of the MenA, MenC, MenW, and MenY response following 2 doses of MenABCWY when administered on a 0- and 12-month schedule, the estimand has the following attributes:

- Population: Participants receiving 2 doses of MenABCWY and who are in compliance with the key protocol criteria (evaluable participants).
- Variable: hSBA titer for each of the ACWY test strains.
- Intercurrent event(s): Participants will be summarized according to the vaccine group to which they were randomized. Missing serology data will not be imputed.
- Population-level summary: The percentage of participants achieving an hSBA titer  $\geq$  LLOQ for each ACWY test strain at 12 and 24 months after the second dose of MenABCWY in Group 1 (0- and 12-month schedule).

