	
5. Had at least 1 valid and determinate MenA/C/W/Y or MenB assay result at 1 month after the second MenABCWY vaccination (Visit 5 for Group 1 and Visit 10 for Group 2).
 
6. Had received no prohibited vaccines or treatment through Visit 5 (Group 1) or Visit 10 (Group 2).
 
7. Had no important protocol deviations through Visit 5 (Group 1) or Visit 10 (Group 2).

Post-Vaccination 1 mITT population	All participants who received at least 1 study vaccination and had at least 1 valid and determinate MenB or MenA/C/W/Y assay result available at any time point from Visit 1 to Visit 2.
Post-Vaccination 2 mITT population	All participants who received at least 1 study vaccination and had at least 1 valid and determinate MenB or MenA/C/W/Y assay result available at any time point from Visit 1 to Visit 5 for Group 1 and from Visit 1 to Visit 10 for Group 2.
Vaccination 1 safety population	This population will include participants who received the first dose of study intervention at Visit 1 and for whom safety information from Visit 1 up to Visit 4 is available in Groups 1 and 2.
Vaccination 2 safety population	This population will include participants who received the second dose of study intervention at Visit 4 (MenABCWY for Group 1, saline for Group 2) and for whom safety information from Visit 4 up to Visit 7 (for Group 1) or Visit 9 (for Group 2) is available.
Vaccination 3 safety population	This population will include participants who received the third dose of study intervention at Visit 9 (MenABCWY for Group 2) and for whom safety information from Visit 9 through Visit 10 is available.
Follow-up safety population 1	This population will include participants who received the first dose of study intervention and for whom safety information from Visit 2 up to Visit 4 in Groups 1 and 2 is available.
Follow-up safety population 2	This population will include participants who received the second dose of study intervention (MenABCWY for Group 1, saline for Group 2) and for whom safety information from Visit 5 up to Visit 7 (for Group 1) or Visit 9 (for Group 2) is available.

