For determination of the evaluable population(s), items 1 through 5 will be computerized checks of the data, while items 6 and 7 will be determined by clinical review. An important protocol deviation is a protocol deviation that, in the opinion of the sponsor's global medical monitor, would materially affect assessment of immunogenicity, eg, participant receipt of a prohibited vaccine or medication that might affect immune response or a medication error with suspected decrease in potency of the vaccine. The global medical monitor from the sponsor will identify those participants with a protocol deviation prior to unblinding of the study.

For participants withdrawn early, they will be included in the respective follow-up population, in case they have any type of AEs in the respective AE follow-up intervals.

For Analysis 1 (per [Section 7.1](#)), the post-Vaccination 1 evaluable population will be fully defined for both Groups 1 and 2. Similarly, the post-Vaccination 2 evaluable population will be fully defined for Group 1 for Analysis 1. The final determination of the protocol

deviations, and hence the post-Vaccination 2 evaluable population for Group 2, will be completed for the final analysis.

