#### **6.2.1.2. hSBA Titer for Each of the Primary MenB Test Strains (A22, A56, B24, and B44), Group 1 (0- and 12-Month Schedule)**

##### **6.2.1.2.1. Main Analysis**

- Estimand strategy: Hypothetical.
- Analysis set: Post-Vaccination 2 evaluable population for Group 1.
- Analysis methodology: Exact 2-sided 95% CIs for the percentages using the Clopper-Pearson method.
- Intercurrent events and missing data: Missing serology results will not be imputed. Participants will be summarized according to the vaccine group to which they were randomized.

- The percentage of participants in Group 1 (0- and 12-month schedule) with hSBA titers  $\geq$  LLOQ for each of the primary MenB test strains at 12 and 24 months after the second dose of MenABCWY will be summarized using the post-Vaccination 2 evaluable population.

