#### **6.2.1.3. hSBA Titer for Each of the MenACWY Test Strains, Group 1 (0- and 12-Month Schedule)**

##### **6.2.1.3.1. Main Analysis**

- Estimand strategy: Hypothetical.
- Analysis set: Post-Vaccination 2 evaluable population for Group 1.
- Analysis methodology: Exact 2-sided 95% CIs for the percentages using the Clopper-Pearson method.
- Intercurrent events and missing data: Missing serology results will not be imputed. Participants will be summarized according to the vaccine group to which they were randomized.
- The percentage of participants in Group 1 with hSBA titers  $\geq$  LLOQ for each of the ACWY test strains at 12 and 24 months after the second dose of MenABCWY will be summarized using the post-Vaccination 2 evaluable population.

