**6.3.1.2. hSBA Titer for Each of the MenACWY Test Strains (After Vaccination 1)****6.3.1.2.1. Main Analysis**

- Estimand strategy: Hypothetical.
- Analysis set: Post-Vaccination 1 evaluable populations for Groups 1 and 2.
- Analysis methodology: Exact 2-sided 95% CIs for the percentages using the Clopper-Pearson method.
- Intercurrent events and missing data: Missing serology results will not be imputed. Participants will be summarized according to the vaccine group to which they were randomized.
- hSBA GMTs for each ACWY test strain at baseline and 1 month after the first dose of MenABCWY for each group, separately and combined, may be summarized.
- The percentage of participants with hSBA titers  $\geq$  LLOQ for each ACWY test strain at 13 months after the first dose of MenABCWY (Group 2 only).
- The percentage of participants achieving at least a 4-fold rise in hSBA titer from baseline for each ACWY test strain at 1 month after the first dose of MenABCWY for each group, separately and combined, may be summarized.
  - For participants with a baseline hSBA titer below the LOD (or an hSBA titer of  $< 1:4$ ), a 4-fold response is defined as an hSBA titer of  $\geq 1:16$ .
  - For participants with a baseline hSBA titer of  $\geq$  LOD (ie, hSBA titer of  $\geq 1:4$ ) and  $<$  LLOQ (ie, an hSBA titer of 1:8), a 4-fold response is defined as an hSBA titer of  $\geq 4$  times the LLOQ.
  - For participants with a baseline hSBA titer of  $\geq$  LLOQ, a 4-fold response is defined as an hSBA titer of  $\geq 4$  times the baseline titer.

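### Group 1 persistence at 12 and 24 months uses an analysis set screened only through Visit 5, and no rule removes a Visit 6 or 7 titre drawn after an outside meningococcal vaccine

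*SAP*

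**What the plan says.** **Membership of the set.** In SAP Section 4, item 6 for the post-Vaccination 2 evaluable population is "Had received no prohibited vaccines or treatment through Visit 5 (Group 1) or Visit 10 (Group 2". Protocol 9.3 has the same cut-off: "had received no prohibited vaccines or treatment through Visit 5 (Group 1) or Visit 10 (Group 2), and". Important protocol deviations are screened to the same visits, and eligibility to one month after the second MenABCWY dose. SAP Section 4 adds that the post-Vaccination 2 "evaluable population will be fully defined for Group 1 for Analysis 1", which takes place once Visit 5 is complete.

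**Use of the set.** Protocol 9.4.1 says Group 1 results "at 12 and 24 months after the second dose of MenABCWY will be summarized using the post-Vaccination 2 evaluable population". SAP 6.2.1.2.1 does the same for MenB ("at 12 and 24 months after the second dose of MenABCWY will be summarized") and SAP 6.2.1.3.1 for ACWY ("for each of the ACWY test strains at 12 and 24 months after the second dose of MenABCWY will be summarized").

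**Estimand.** Protocol 9.1.1 targets the effect had participants followed the protocol, and the SAP labels both persistence analyses hypothetical. In SAP 2.1.5 the intercurrent-event attribute for persistence says only: "Participants will be summarized according to the vaccine group to which they were randomized. Missing serology data will not be imputed".

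**Prohibitions and recording.** Protocol 6.5.1 prohibits nonstudy meningococcal vaccines, and blood products in the 6 months before any draw. Protocol 6.5 requires nonstudy meningococcal vaccines to be collected to the end of participation.

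**Same pattern elsewhere.** SAP 6.3.1.2.1 reports the percentage at or above "LLOQ for each ACWY test strain at 13 months after the first dose of MenABCWY (Group 2 only" in the post-Vaccination 1 evaluable set, which is screened only through Visit 2.

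**The concern.** Group 2 is screened through Visit 10, its last analysed draw. Group 1 is analysed at two visits beyond its screening horizon. A participant who gets an outside meningococcal vaccine after Visit 5 and is still sampled remains in the set, and the new titre counts as persistence after two doses of MenABCWY. The exposure is plausible: entry age is 11 to under 15, and Protocol 2.1 cites a routine MenACWY booster at 16.

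For the strains covered by the outside vaccine, the percentage would mix persistence with a fresh response. That is not the quantity the hypothetical strategy names. What is at stake is the accuracy of a stated secondary objective and, to a lesser degree, of one exploratory Group 2 summary. No hypothesis or decision rule depends on either.

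**Working it through.** **1. Length of the unscreened period (visit windows, Protocol 1.3).** Visit 5 is 28 to 42 days after Visit 4.
- To Visit 6 (336 to 394 days after Visit 4): 336 − 42 = 294 to 394 − 28 = 366 days. With the 60-day extension in Protocol 8.11.1.6: 454 − 28 = 426.
- To Visit 7 (700 to 756 days after Visit 4): 700 − 42 = 658 to 756 − 28 = 728 days.
- Group 2, Visit 2 to Visit 5: 336 + 28 − 42 = 322 to 394 + 42 − 28 = 408 days.

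**2. Does another rule close the gap?**
- SAP 5.3.2 makes a result missing only if serum was insufficient, the result was indeterminate, the assay was not done, or no blood was drawn. SAP 3.3 derives the binary variables the same way.
- The mITT sets have no exclusion for prohibited vaccines.
- SAP 6.5.4 lists nonstudy vaccines but removes nobody.
- The estimand attribute in SAP 2.1.5 does not mention outside vaccination.

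None of these removes a titre already drawn.

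**3. The plan's own precision (Protocol Table 4).** n = 150 × (1 − 0.20) = 120. Exact Clopper-Pearson half-widths at 60, 70, 80 and 90% are 9.09, 8.53, 7.51 and 5.77 points, which match the stated 9.1, 8.5, 7.5 and 5.8.

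**4. Size of the bias.** Let f be the share vaccinated outside the study before the draw, r the percentage of them at or above LLOQ afterwards, and p true persistence. Then bias = f × (r − p), which is zero if r = p. The documents give neither f nor p for this regimen. With r = 95% (assumed):

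| f (assumed) | p = 60% | p = 80% |
|---|---|---|
| 2% | +0.7 | +0.3 |
| 5% | +1.75 | +0.75 |
| 10% | +3.5 | +1.5 |

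As an upper bound, take r = 100%, so bias = f × (1 − p). At f = 10% and p about 60%, keeping the titres gives 77/120 = 64.2% (95% CI 54.9 to 72.7), and removing them gives 65/108 = 60.2% (50.3 to 69.5). At f = 20% and p = 40% the bound is +12 points.

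**5. An illustrative MenB benchmark.** Assume entry age is uniform over 11 to under 15. The share who have reached 16 at t years from Visit 1 is (t − 1)/4.
- Visit 6: 25% at t = 2 (21 to 29% over days 672 to 788). With the 60-day extension: 848/365.25 = 2.32 years, so 33%.
- Visit 7: 50% at t = 3 (46 to 54% over days 1036 to 1150).

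Multiply by the 17.2% MenB coverage at age 17 (Protocol 2.2.1): f = 0.25 × 17.2% = 4.3% at Visit 6 and 0.50 × 17.2% = 8.6% at Visit 7. For p, use the 57.5% to 82.8% that Protocol 2.2.2.1 reports up to 2 years after a Trumenba booster, a different regimen.
- Visit 6: 4.3% × (95 − 57.5)% = +1.6 points, down to 4.3% × (95 − 82.8)% = +0.5.
- Visit 7: 8.6% × 37.5% = +3.2 points, down to 8.6% × 12.2% = +1.0.

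**6. Group 2 at Month 13.** Visit 5 falls 364 to 436 days after Visit 1, so (t − 1)/4 gives 0 to 5% reaching 16. Uptake linked to the age-16 booster is likely very small there. The Group 2 MenB summary at Month 13 uses the set screened through Visit 10 and is not affected.

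**The case against.** The strongest reply is that study conduct will deal with most cases. Protocol 6.5 calls an outside meningococcal vaccine exclusionary. Sites confirm continued eligibility and the withdrawal criteria at Visits 6 and 7 before drawing blood, and protocol violation is a listed reason for discontinuation. A participant withdrawn before sampling has no titre and is already missing under SAP 5.3.2. This narrows the problem to cases not withdrawn or found after the draw. It does not close it: withdrawal is not mandated, and no analysis consequence is attached. Protocol 7.2 also asks a withdrawing participant to return, if applicable, for a final visit with the next visit's procedures, which at Visit 6 include a draw.

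Second, the outbreak allowance in Protocol 6.5.2 has no meningococcal exception, so the prohibition in 6.5.1 may not be absolute. The two passages must be reconciled. If outbreak use is allowed, a retained titre becomes more likely.

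Third, the size rests on assumptions. This stands. The benchmark covers MenB, whereas the routine dose cited at 16 is MenACWY. It applies coverage among 17-year-olds to everyone who has reached 16. It also ignores that participants have already had two MenB-containing doses and are told not to have outside vaccine. It probably overstates MenB uptake and does not measure the ACWY route.

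Finally, recorded nonstudy vaccines will be listed, so those cases would be visible. A listing does not correct the percentage.

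**Conclusion.** The gap is real and lies in both documents. Following the plan as written keeps a Visit 6 or 7 titre drawn after a prohibited vaccine, or after a blood product inside the 6-month limit, contrary to the stated hypothetical strategy. The bias is upward whenever response after the outside vaccine exceeds true persistence, and it affects only the strains that vaccine covers.

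Its size cannot be known from the documents. With assumed uptake of 2 to 10% and 95% response, it is about 0.3 to 3.5 points for true persistence of 60 to 80%, within the planned half-widths of 9.1 and 7.5 points. Only uptake well above that range, with low persistence, would exceed them. Severity is minor: descriptive secondary and exploratory summaries are affected, and the primary and safety analyses are not.

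A separate, smaller point is that Visit 7 has no step to record nonstudy vaccinations in the Group 1 schedule or Protocol 8.11.1.7, although Protocol 6.5 requires collection to the end of participation. This is a risk of missed data, not evidence of loss.

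**What to change.** In SAP Section 4, define 12-month and 24-month persistence evaluable sets: post-Vaccination 2 evaluable, plus no nonstudy meningococcal vaccine, no blood product in the 6 months before the draw, and no important deviation, through Visit 6 or Visit 7 respectively. Defining the vaccine criterion by receipt covers outbreak use as well. Alternatively, set titres after such an event to missing. Use these sets in 6.2.1.2 and 6.2.1.3, and keep the current set as a sensitivity analysis. Screen the Group 2 Month 13 ACWY summary in 6.3.1.2 through Visit 5. While redrafting, say how Visit 6 and 7 draws outside their windows are handled, since item 4 checks Group 1 draw timing only at Month 0 and Visit 5.

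The SAP should note the departure from Protocol 9.4.1, which Protocol Section 9 permits. The cost is a little precision: with 5% excluded (120 to 114) the exact half-width goes from 9.1 to 9.3 points at 60% and from 7.5 to 7.7 at 80%; with 10% excluded (108) it goes to 9.6 and 8.0. The extra deviation review would follow unblinding, as it already must for Group 2, so recorded dates should decide where possible.

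Separately, reconcile the Group 1 schedule and 8.11.1.7 with Protocol 6.5 on recording at Visit 7. Changing the protocol text needs an amendment with IRB/EC approval; a reminder to sites of the existing requirement could come first.
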